3.2 Investigational Product (treatment, device) and Indication

Not applicable.

3.3 Preclinical Evidence

Not applicable.

3.4 Clinical Evidence to Date

Diffusion-weighted imaging is an MRI procedure that generates images of biological tissues in which water diffusion is exponentially related to signal intensity (brightness)^{40,41}. Originally used only for brain imaging to detect early signs of stroke and other brain abnormalities, diffusion-weighted MRI now has many applications within the musculoskeletal system that are increasing the knowledge of diagnosis and intervention³⁸.

Intravoxel incoherent motion (IVIM) is a method to separate microcirculatory effects from thermal diffusion effects in diffusion-weighted MRI.¹⁹ IVIM offers a way to study microcirculatory blood-flow properties directly, without intravenous contrast injection. In the past years, studies validating the IVIM method to measure perfusion have accumulated due to major advancements seen in MR hardware, pulse design and post-processing capabilities. The role of IVIM in the musculoskeletal tissue is not yet entirely clear.

A study by Beattie et al.¹⁷ suggests that differences in a patient's reported pain intensity following a single SMT intervention are related to changes in the rate of diffusion of water in the intervertebral discs of the upper lumbar spine and the lumbosacral junction. The results of the study are consistent with previous observations by the same authors of a significant interaction between subject responses to a single treatment of manual pressures followed by prone press-up exercises administered to patients with LBP¹⁶.

3.5 Dose Rationale / Medical Device: Rationale for the intended purpose in study (pre-market MD)

Not applicable.

3.6 Explanation for choice of comparator (or placebo)

The intervention and control procedure differ only in the administration of a high-velocity, low-amplitude SMT intervention for the intervention group. The control procedure therefore is chosen to be identical to the intervention procedure with the exception that tissue pressure and thrust are not administered to the spinal segment. This ensures that there is minimal confounding due to position changes and human touch.

3.7 Risks / Benefits

SMT is commonly associated with transient minor musculoskeletal harms such as muscle soreness and local discomfort, although they may be equally common following non-SMT manual therapy¹. Case reports and systematic and nonsystematic reviews have included discussion of serious harms and adverse events following SMT in general and following SMT for low back pain. Examples of reported serious adverse events following lumbopelvic SMT intervention include cauda equina syndrome, lumbar disk herniation, fracture, and spinal hematoma⁴². However, these reports were not able to assess causality or calculate the incidence of serious adverse events following SMT^{1,43}.

In a recent systematic review and metaanalysis, SMT interventions for acute low back pain were associated with statistically and clinically significant benefit in pain and function at up to 6 weeks¹. The size of the effect on pain is about the same as for nonsteroidal anti-inflammatory drugs in acute low back pain, according to a Cochrane review on this topic⁴⁴. For chronic back pain, there is evidence that SMT has a statistically significant but not clinically relevant effect on pain relief and functional status compared to other interventions⁴². All SMT interventions in this study will be performed by experienced Doctors of Chiropractic with over 10 years of clinical experience. Contraindications for SMT interventions will be strictly monitored at baseline.

There are no known health hazards from temporary exposure to the MR environment. The MR environment does involve a strong static and pulsed magnetic field, as well as radiofrequency energy. Specific safety concerns concerning these factors must be taken into account. Patients are not exposed to the harmful effects of ionizing radiation, as MR images are obtained without the use of ionizing radiation.

Ferromagnetic objects brought into the static magnetic field may cause damage to the scanner or injury to the patient or medical professionals, as those objects may become projectiles. Careful screening of people and objects entering the MR environment is obligatory⁴⁵.

3.8 Justification of choice of study population

Patients included in this study are persons over 18 years and below 75 years of age with low back pain of a duration of more than 4 weeks clinically not attributable to “red flags” (i.e., infection, trauma, fractures, inflammatory spondylarthropathies). This corresponds to the patient population typically treated in chiropractic practices in Switzerland⁴⁶. Controls are healthy participants over 18 and below 75 years of age who have not suffered from low back pain in the last year and have never experienced low back pain for longer than 7 consecutive days. Patients and controls provide informed consent before inclusion into the study. No vulnerable participants will be included in this study. Study Objective

3.9 Overall Objective

The purpose of our study is to assess and quantify changes in diffusion and perfusion within the intervertebral disc and adjacent spinal muscle tissues of a lumbar spinal segment receiving spinal manipulative intervention.

3.10 Primary Objective

The primary objective is to measure the change in diffusion and perfusion on diffusion-weighted and IVIM MRI in the intervertebral disc and adjacent spinal muscle tissue of a lumbar spinal segment following a lumbar SMT intervention or control intervention to that segment.

3.11 Secondary Objectives

Secondary objectives are to determine if diffusion and perfusion changes in DWI and IVIM-MRI are dependent on the severity of degenerative changes classified according to the Pfirrmann- and Weishaupt-Classification; to establish the relationship between clinical baseline parameters and diffusion and perfusion changes in DWI and IVIM-MRI and to determine the repeatability of IVIM-MRI in assessing perfusion changes, as well as assessing diurnal changes in perfusion and diffusion parameters in spinal tissues of healthy controls. Additionally, the presence of several pro- and anti-inflammatory markers in blood will be assessed in patients and controls.

3.12 Safety Objectives

Not applicable as the methods are used according to their certification and labelling, respectively.

4. STUDY OUTCOMES

4.1 Primary Outcome

Changes in diffusion in intra- and extracellular compartments (D), apparent diffusion coefficient (ADC), perfusion in capillaries (D^*) and volume fraction of capillary perfusion (f) in the intervertebral disc and adjacent spinal muscle tissue in patients before and after an SMT- or control intervention and in controls before and after 20 minutes of lying supine.

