
Objectives:	
The main objective of this study is to quantify changes in diffusion and perfusion in the intervertebral disc and adjacent spinal muscle tissue of a spinal segment receiving SMT or control intervention and to evaluate whether those changes differ in spinal segments with or without degenerative changes in low back pain patients.
 
The second study objective is to evaluate the repeatability of IVIM-MRI for quantifying perfusion changes in musculoskeletal tissues and to assess diurnal changes in perfusion and diffusion parameters in spinal tissues as a positive control.

Outcomes:	
The primary study outcome is the change in diffusion (ΔADC) and perfusion (Δ perfusion fraction, Δ pseudodiffusion coefficient) parameters measured on DWI and IVIM MRI in the intervertebral disc and adjacent spinal muscle tissue of a lumbar spinal segment following a lumbar SMT or control intervention to that segment, or, for controls, after 20 minutes of lying in supine resting position.
 
Secondary outcomes are the repeatability and diurnal changes of diffusion- and perfusion-weighted MRI parameters in musculoskeletal tissue in controls, the severity of degenerative changes classified according to the Pfirrmann- and Weishaupt-Classification on MRI, clinical baseline parameters, pro- and anti-inflammatory markers in the obtained blood samples and changes in pain intensity on a numerical pain rating scale after the intervention.

Study design:	Randomized controlled clinical trial

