10.1 Hypothesis

Intervertebral discs and adjacent spinal muscle tissue of the lumbar spine will show a change in the apparent diffusion coefficient and perfusion coefficient on MRI after an SMT intervention.

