10.2 Determination of Sample Size

N = 70 (25 per patient group, 20 controls). Rationale: Based on the study results by Wong et al.¹⁸, we expect an increase in ADC values of at least 6.5% (CI: 3.88%-9.13%) in receivers of SMT-intervention compared to no change in the control-intervention group. 25 patients per group will provide a power of 0.8 (1-beta) to detect an effect of 0.9 at an alpha-level of 0.05⁴⁸. Additionally, the repeatability of IVIM-MRI on musculoskeletal tissue will be assessed in 20 control subjects.

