10.3.2 Primary Analysis

Our hypothesis is that a spinal segment receiving an SMT-intervention will show a change in the diffusion and pseudodiffusion coefficient that is significantly higher than a spinal segment receiving a control intervention. Distributions of the ADC and perfusion coefficient obtained before and after intervention will be tested for the assumptions of normality using the Shapiro-Wilk test. In case of non-normality, data transformation will be used to normalize data. Should this not be possible, non-parametric tests will be used. Two separate repeated measures analysis of variance (ANOVA) will be used to test for effects of time (pre- vs. post-intervention) on ADC and perfusion coefficient with intervention (experimental vs. control intervention) and group (degenerated vs. non-degenerated painful segments) as the between-subject variables.

The PI will supervise the primary analysis as described above. It will be analyzed using SPSS (version 23) at the end of the recruitment period and after obtaining all necessary data.

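### Several unranked primary measures, two primary ANOVAs, a sample size for ADC alone, and no rule for what counts as success

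*Combined protocol and SAP*

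**What the plan says.** Five places describe what is primary, and they do not match.

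- **Section 4.1** lists "Changes in diffusion in intra- and extracellular compartments (D), apparent diffusion coefficient (ADC), perfusion in capillaries" (D*) and the capillary volume fraction (f), in disc and adjacent muscle. That is 4 × 2 = 8 parameter-by-tissue measures, with no order among them.
- **Synopsis, Outcomes** names three changes (ADC, perfusion fraction, pseudodiffusion coefficient) as "parameters measured on DWI and IVIM MRI in the intervertebral disc and adjacent spinal muscle tissue". D is not listed.
- **Section 3.10** gives diffusion and perfusion equal standing: "The primary objective is to measure the change in diffusion and perfusion on diffusion-weighted and IVIM MRI".
- **Section 10.1** predicts that "Intervertebral discs and adjacent spinal muscle tissue of the lumbar spine will show a change in the apparent diffusion coefficient and perfusion coefficient" once SMT has been given, so it names two parameters and both tissues.
- **Section 10.3.2** predicts that the treated segment "will show a change in the diffusion and pseudodiffusion coefficient that is significantly higher than a spinal segment receiving a control intervention". It then states: "Two separate repeated measures analysis of variance (ANOVA) will be used to test for effects of time". The two variables are ADC and a perfusion coefficient. The between-subject factors are intervention and degeneration. Tissue is neither a factor nor specified.

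Section 10.2 gives an expected effect for one variable only: "we expect an increase in ADC values of at least 6.5" per cent with SMT, against no change with the control intervention. It sets alpha at 0.05 and adds that "25 patients per group will provide a power of 0.8 (1-beta) to detect an effect of 0.9 at an alpha-level of" that value. It names no tissue and gives no perfusion effect. Nowhere is there a multiplicity adjustment, a testing order or a success rule.

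**The concern.** The alpha of 0.05 and power of 0.8 in section 10.2 describe a single ADC test, but the primary analysis has at least two tests. What those two figures mean for the trial depends on a rule that is not written.

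- If a significant result on either variable supports the hypothesis, the overall type I error is above 0.05.
- If both must be significant, error is controlled. The power is then unknown, because the plan states no perfusion effect, and a clear ADC result could not stand alone.

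The choice of tissue adds to this. Each ANOVA could be run in disc, in muscle or in both, so two is the smallest count of tests. Without a written rule, the success criterion and the tissue could be settled after results are known.

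**Working it through.** **Inputs from section 10.2:** 25 per arm, effect 0.9, alpha 0.05, power 0.8, for ADC. **Number of tests from section 10.3.2:** two.

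**Assumptions:** the effect of 0.9 is a standardised difference d; tests are two-sided; the time-by-intervention test is treated as a two-sample t test on change scores; all 25 per arm are analysed. The documents give no correlation between the two test statistics, so 0 to 0.9 is shown.

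**1. The plan's own power.** Noncentrality = 0.9 × √(25/2) = 3.18, with 48 degrees of freedom and critical t = 2.01. Power = 0.877, not the stated 0.8. (Using 46 degrees of freedom for the factorial model gives 0.876.) Power of 0.8 at d = 0.9 needs 21 per arm, where it is 0.812. With 25 per arm, 0.8 corresponds to d of about 0.81. At alpha 0.025, 25 per arm gives 0.804.

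**2. Either test counts, each at 0.05.**

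- Independent: 1 − (1 − 0.05)² = 0.0975.
- Correlated: 1 − P(|Z₁| < 1.96 and |Z₂| < 1.96), bivariate normal, gives 0.091 at correlation 0.5 and 0.070 at 0.9.
- Each variable tested in both tissues, four independent tests: 1 − 0.95⁴ = 0.185.

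**3. Both tests required, each at 0.05.** A false claim needs at least one true null hypothesis to be rejected, so error is at most 0.05. If both nulls are true and the tests are independent, it is 0.05² = 0.0025.

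Joint power with ADC at d = 0.9 and 25 per arm (perfusion effects are assumed):

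| Perfusion d | Correlation 0 | 0.5 | 0.9 |
|---|---|---|---|
| 0.9 | 0.77 | 0.80 | 0.84 |
| 0.7 | 0.60 | 0.64 | 0.68 |
| 0.5 | 0.36 | 0.40 | 0.41 |

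For the first cell, 0.877 × 0.877 = 0.77. At perfusion d = 1.0 the range is 0.82 to 0.87.

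If the stated 0.8 held for each test instead of 0.877, joint power would be 0.8 × 0.8 = 0.64 for independent tests and 0.75 at correlation 0.9.

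**4. Size needed for joint power 0.8.** With ADC at d = 0.9, perfusion at d = 0.7 needs 34 to 36 per arm over the same correlations, and d = 0.5 needs about 64.

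**The case against.** **Both may be required.** The hypotheses in 10.1 and 10.3.2 join diffusion and perfusion with *and*. On that reading error never exceeds 5%, so a reader should not infer that the trial certainly runs at 9.75%. This stands as a possible reading. However, neither sentence is a decision rule, the ANOVAs are described as separate, and the reading leaves power resting on an unstated perfusion effect.

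**The trial may already be sized for two tests.** Power at 0.025 is 0.804, which matches the stated 0.8. But 10.2 states 0.05 and no split is written, so the match cannot be taken as a planned adjustment.

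**The perfusion variable is not a free choice.** A reader might infer that it could be any parameter. Section 4.1 describes D* as perfusion in capillaries and f as a volume fraction, and the hypothesis sentence in 10.3.2 says pseudodiffusion. D* is the natural reading; the label needs harmonising.

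**Eight measures do not mean eight primary tests.** Independent testing of all eight would give 1 − 0.95⁸ = 33.7%, but 10.3.2 plans two ANOVAs, so the documents do not support that figure.

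**There are safeguards.** The radiologist is blinded (5.2.2), unblinding waits until the last participant is included (5.3), and departures from the statistical plan are reported as amendments (10.3.4). These reduce the scope for choosing after the fact, but they do not supply the missing rule.

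**This is a mechanistic study.** Its objectives are to measure and quantify. Even so, it states a significance hypothesis with an alpha and a power, and those need a defined endpoint.

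**Conclusion.** The concern holds: outcome list, analysis and sample size do not match, and the success rule is missing. It should be fixed.

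If either test counts, the false-positive risk is 9.75% for independent tests and 7.0% at an assumed correlation of 0.9, or 18.5% for four independent tests across both tissues. If both are required, error is at most 5%. Joint power is then near 0.8 only if the perfusion effect is about 0.9 or more.

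It would go too far to call the trial underpowered for perfusion, because no perfusion effect is given to judge against. The power figures also depend on reading 0.9 as a standardised difference and on the recomputed 0.877, which departs from the stated 0.8. They assume complete data: at 22 per arm, single-test power falls to 0.83.

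**What to change.** Before unblinding:

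1. Make the between-arm difference in ADC change at the treated segment, in one named tissue, the single primary endpoint at two-sided 0.05. The disc is the candidate: the synopsis background and section 3.1 cite the sample-size source for diffusion change in discs. The sponsor should confirm this.
2. Test D* in one named tissue second, at 0.05, only if ADC is significant. Total error across the two tests stays at 5%, and ADC keeps its full power.
3. Move the other parameter-by-tissue measures to secondary, and use one endpoint list in the synopsis, 3.10, 4.1, 10.1 and 10.3.2.

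If both variables are to stay co-primary, write one rule. Where either may count, test each at 0.025 (power 0.804 each at d = 0.9). Where both are required, restate the power with a stated perfusion effect, since it may fall below 0.8 at 25 per arm.

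**Cost.** The fixed sequence needs no extra patients or scans, and nor does the 0.025 split at d = 0.9. The both-required option may need more patients. The other measures lose primary status. Under the fixed sequence, perfusion cannot be claimed when ADC is not significant: about 12% of the time at d = 0.9 with all 25 per arm analysed (1 − 0.877), or 20% at the stated power. A substantial amendment under 2.10 may be needed.

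**Separate point.** Name the scan or summary used as the post value. The synopsis and 5.1 give patients three post-intervention scans, while 10.3 uses two time points. The single second round in 8.3.2 could be read as one re-entry containing all three scans, so this may be an omission rather than a contradiction.

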4.2 Secondary Outcomes

Secondary outcomes are the repeatability and diurnal changes of diffusion- and perfusion-weighted MRI parameters in musculoskeletal tissue in controls.

4.3 Other Outcomes of Interest

The severity of degenerative changes classified according to the Pfirrmann- and Weishaupt-Classification on MRI, clinical baseline parameters, pro- and anti-inflammatory markers in the obtained blood samples, change in disability and pain intensity on a numerical pain rating scale after the intervention.

4.4 Safety Outcomes

Not applicable.

5. STUDY DESIGN

5.1 General study design and justification of design

This study is designed as a prospective randomized controlled clinical trial. 50 persons over 18 and below 75 years of age with low back pain of more than 4 weeks without any “red flags” (i.e., infection, trauma, fractures, inflammatory spondylarthropathies) as well as 20 asymptomatic controls meeting the inclusion criteria are included. Study visits will take place in the morning at the same time.

Patients and controls report baseline information and receive a standardized baseline examination. Patients’ skin above the interspinous ligament causing the most pain upon palpation by the examiner is marked with a pen. The examiner is blinded to the intervention that follows.

Patients and controls are evaluated in the MRI-Scanner lying supine prior to intervention. The radiologist will perform a preliminary viewing of the MRI sequence to screen for contraindications to SMT (e.g. tumors, infection, fractures, severe nerve compression). Patients with contraindications for SMT will be excluded from the study.

Patients will be randomized using stratified randomization to receive either an SMT intervention in right and left side-lying position at the segment of the marked interspinous ligament, or receive a control intervention in right and left side-lying position. The chiropractor administering the intervention is blinded to clinical and radiological information. After this, patients undergo 3 sequential MR-imaging rounds. Once imaging is complete, the subjects exit the scan room and provide information on post-intervention pain-intensity.

MRI-quantified changes in diffusion and perfusion of intervertebral discs with and without degenerative changes and of adjacent spinal muscle tissue after SMT intervention are assessed and compared between patients and controls.

In order to assess the repeatability of IVIM imaging in quantifying perfusion in musculoskeletal tissues, 20 controls will undergo a separate procedure consisting of a baseline diffusion- and perfusion-weighted MRI, which is repeated after 20 minutes of lying in a supine position. In order to assess diurnal changes in perfusion and diffusion parameters in musculoskeletal tissue, controls will present for a third MRI approximately 10 hours later, after partaking in activities of daily life as normal, but excluding strenuous physical activity.

Patients will be contacted by telephone at one week, one month and three months after the intervention. Their global impression of change will be assessed. Type and quantity of concomitant therapies and interventions will be assessed. The Oswestry Disability Index and painDetect questionnaires will be repeated.

5.2 Methods of minimizing bias

5.2.1 Randomization

Patients are subdivided into strata in order to balance for age and sex, then permuted block randomization is used for each stratum to assign patients to receive either SMT or control intervention.

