6.3 Assignment to study groups

Patients are subdivided into strata in order to match for age, sex, and degenerative changes, then permuted

block randomization is used for each stratum to assign patients to receive either SMT or control intervention. Randomization is performed by an investigator not involved in the examination using sequentially numbered sealed opaque envelopes.

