8.3 Procedures at each visit

8.3.1 Visit 1

- Patient screening and eligibility assessment in the Polyclinic for Chiropractic Medicine by an Investigator
- Patient will be contacted and asked if he would like to participate 3-4 days after screening.
- Patient is sent informed consent and general consent, which he will return signed.
- An appointment is made for Study Visit 2

- Controls will contact one of the investigators by the number provided on the flyer. Control is sent informed consent and general consent, which he will return signed. An appointment for study visit 2 is made.

8.3.2 Visit 2

- Inclusion and exclusion criteria are checked.
- Demographics and baseline Information is collected by an Investigator. Oswestry Disability Index and painDetect questionnaires are administered.
- A physical examination including vital signs, lower extremity neurological examination, and lumbar spine examination is performed by an Investigator.

- Subjects consenting to venipuncture will proceed to the venipuncture site, where 10-15 ml of whole blood will be drawn from the vein (usually at the elbow) using serum collection tubes. Blood samples are allowed to clot at room temperature for 30-60 min and then centrifuged at 2500 x g for 10 min at 4°C. The resulting serum supernatant is stored in aliquots at Balgrist Campus first at -20°C and transferred within 2-20 hours to -80°C.
- Subjects will prepare for MRI, which will be performed under the supervision of a radiographer. The first sequence of MR-imaging takes approximately 20 minutes.
- Randomisation takes place.
- Patients exit the scanner and receive either an intervention or a control intervention, depending on the randomisation result.
- Controls exit the scanner and lie supine for 20 minutes.
- All subjects reenter the scanner and proceed to have a second round of imaging.
- Patients are assessed for pain and vital signs. They may then leave the study site.
- Controls may also leave the study site, and go on to lead their normal daily lives (excluding strenuous physical activity) for the next 10 hours. They then report back to the University Hospital Balgrist for their third and last MRI. After this, they are also assessed for pain and vital signs. This marks the end of the study for controls.

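### Sections 5.2.1 and 6.3 give different stratification factors, and age and sex, which are strata in both, are absent from the primary model; any resulting error is conditional and conservative

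*Combined protocol and SAP*

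**What the plan says.** Section 5.2.1 states: "Patients are subdivided into strata in order to balance for age and sex". Section 6.3 states: "Patients are subdivided into strata in order to match for age, sex, and degenerative changes". Both then use permuted blocks within strata, and 6.3 adds sequentially numbered sealed opaque envelopes. Section 5.1 says only that randomisation is stratified, without naming factors. No age cut-off, degeneration threshold or block size is given.

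Section 10.3.2, like 10.3, plans repeated-measures ANOVAs to "test for effects of time (pre- vs. post-intervention) on ADC and perfusion coefficient". The only other terms that these models are given are two factors that vary between patients; the section specifies the analysis "with intervention (experimental vs. control intervention) and group (degenerated vs. non-degenerated painful segments) as the between-subject variables". Neither section has a term for age or sex, and no other section mentions adjustment for strata.

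On timing, 5.1 describes the first scan, then a viewing ("The radiologist will perform a preliminary viewing of the MRI sequence to screen for contraindications to SMT"), then exclusion of patients with contraindications, then randomisation. The bullet list in 8.3.2 goes from the first MRI to "Randomisation takes place". Section 8.2.3 gives the grading of degeneration to a radiologist but does not say when it is done.

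**The concern.** There are two separate issues.

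**Allocation.** The two lists call for different sets of envelopes. Under 6.3 the envelope cannot be picked until degeneration has been graded on the first MRI, and no section puts that grading before allocation. Under 5.2.1 the split of degenerated segments between arms is left to chance, although the synopsis makes the comparison of degenerated and non-degenerated segments part of the main objective.

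**Analysis.** Stratifying on a factor that predicts the outcome reduces the true sampling variance of the treatment effect. A model that leaves the factor out does not see this reduction, so its standard error is too large. At stake is some power in a trial of 50 randomised patients, and a test that runs below its nominal 5%.

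**Working it through.** **Inputs from the documents.** 25 patients per arm, effect 0.9 (read as a standardised difference), alpha 0.05, power 0.8 (10.2); strata from 5.2.1 and 6.3; model terms from 10.3.2.

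**Inputs assumed, because the documents do not give them.** Two levels per factor, each level equally likely; blocks of 4; two-sided testing; and R², the share of variance of the pre-post change that the factors explain, taken over a range.

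**Step 1: the plan's own figure.** A two-sample t-test with 25 per arm has non-centrality 0.9 × √(25/2) = 3.18 and two-sided power 0.877. The stated inputs therefore give more than the stated 0.80. That is a different matter from this point; 0.877 serves here only as the reference value.

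**Step 2: what the planned test uses.** With one pre and one post value, the intervention-by-time test is a test on within-patient change. Effects of age and sex on the level of ADC cancel. Only their effects on the change matter.

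**Step 3: standard error.** With perfect balance on age and sex, the model's standard error would exceed the true one by a factor of 1/√(1 − R²): 1.05 at R² = 0.1, 1.12 at 0.2 and 1.20 at 0.3. Incomplete blocks make the balance imperfect, so simulation gives somewhat less. In the table R² refers to age and sex only. Ranges cover the two strata lists, and the first two result columns come from runs with no treatment effect.

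| R² | Standard error too large by | Type I error, planned model | Power at 0.9, planned model | Power at 0.9, plus age and sex |
|---|---|---|---|---|
| 0 | about 0% | about 5% | 0.86–0.87 | 0.86–0.87 |
| 0.1 | 4–6% | 4–4.5% | 0.87–0.88 | 0.89–0.90 |
| 0.2 | 9–10% | 3–3.5% | 0.88–0.89 | 0.93 |
| 0.3 | 15–16% | about 2.5% | 0.89–0.90 | 0.95–0.96 |

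**Step 4: all three factors predictive.** Let age, sex and degeneration have equal effects and jointly explain 15% / 30% of the variance of change. Type I error of the planned model is about 4% / 3%. Power at 0.9 SD is about 0.90 / 0.92 without age and sex, and about 0.92 / 0.95 with them. Repeat runs differ by about 0.01.

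**Step 5: does the conflict between the lists move the standard error?** Hardly. The results in Steps 3 and 4 are similar under either list, because degeneration, the disputed factor, is already in the model.

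**Step 6: balance on degeneration.** If half of segments are degenerated, the arms differ by 6 or more degenerated segments in about 13% of allocations when degeneration is not a stratum, against 0.2% when it is. Take a difference of exactly 6, 11/25 against 17/25. The overall proportion is 28/50 = 0.56, and the correlation with arm is 0.24 × 0.5 / √(0.56 × 0.44) = 0.24. The variance inflation is 1/(1 − 0.24²) = 1.06, so the standard error is √1.06 = 1.03 times as large, an increase of about 3%.

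**Step 7: size of strata.** Two binary factors give 4 strata averaging 50/4 = 12.5 patients. Three give 8 strata averaging 50/8 = 6.25, or about one and a half blocks of 4.

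**The case against.** The strongest reply is that the planned primary test is valid. It works on change, the documents contain no evidence on how far age or sex predicts change, and at the planned effect its power stays above 0.80 in every setting examined. All of this stands. A cited traction study, by its title, found age-related differences in disc response. That makes some dependence on age plausible, but it supplies no figure. Adding age and sex is thus a gain in efficiency and does not rescue a faulty test.

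A second reply is that chance imbalance in degeneration is adjusted for by the model. This also stands, and it reduces the 13% figure to a small loss of precision.

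A reader might also infer from 8.3.2 that the contraindication check could follow allocation and so produce post-randomisation exclusions. The documents do not support this. Section 5.1 puts the viewing and the exclusion before randomisation, and 6.4 lists contraindications found on the first MRI among the reasons for exclusion from enrolment. Section 8.3.2 omits the viewing but does not place it later. What remains is narrower: no section says that degeneration is graded before allocation.

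**Conclusion.** The contradiction between 5.2.1 and 6.3 is plain on the text and needs no assumption: as written, the allocation cannot be implemented unambiguously. It is also certain that the primary model omits two factors that are strata under either list.

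The statistical consequence of that omission is conditional. It ranges from none, if age and sex do not predict change, to the modest conservatism and power loss shown in Step 4. It rests on the assumed number of levels, block size and explained variance.

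Two stronger readings should be resisted. One is that the standard error is wrong whatever the data; it is wrong only if age or sex predicts change, and then in the conservative direction. The other is that the conflict between the lists is what disturbs the standard error; its effect is on envelope preparation, the timing of grading, balance and sparse strata. The correction is worth making because it is nearly free, and it should be made before the envelopes are prepared.

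**What to change.** 1. **Sections 10.3 and 10.3.2:** add age and sex as covariates beside degeneration. Enter them with their interaction with time, so that they act on the change. Cost: about two degrees of freedom if each is a single term, and almost no power if they turn out not to predict change.
2. **Sections 5.2.1 and 6.3:** state one identical strata list, with the age cut-off, the degeneration threshold on the named classifications, and the block size. The threshold is also needed to define the group factor in the model. In choosing, weigh the sparseness of 8 strata against the small precision loss from leaving degeneration unstratified. Cost: wording.
3. **Section 8.3.2, if degeneration is kept as a stratum:** state that it is graded on the first MRI and recorded before the envelope is opened, for example at the radiologist viewing that 5.1 already places before randomisation. Cost: a grading step while the patient waits. The documents give no figure for how long this takes, so its feasibility should be confirmed with the radiologist.
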